10.5 Withdrawal of individual subjects

Subjects can leave the study at any time for any reason if they wish to do so without any consequences. The investigator can decide to withdraw a subject from the study for urgent medical reasons.

10.6 Replacement of individual subjects after withdrawal

Individual subjects will be replaced after withdrawal if the transplantation procedure is cancelled.

10.7 Other reasons for going off study

- Death
- Major protocol violation
- Graft failure
- Relapse/progression

Patients who are withdrawn from the study treatment for other reasons than death will be followed only for overall survival. Data obtained from patients who are withdrawn from the study treatment for other reasons than withdrawal of their consent will be used for statistical analysis.

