10.3.3 Post-treatment follow-up

After completing the treatment period and discharge from the hospital, all subjects will be followed in the Post Treatment Follow-Up period. Counting from Day 0 (= day of HPC(A) infusion) until Day 100.

If a patient prematurely discontinues the study because of any reason before Day 100 all assessments planned for the regular Day 100 visit should be performed at time of discontinuation. This visit will be registered in the EDC system as an early termination visit.

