10.3.4 Long term follow-up

All enrolled subjects will be followed in the long term follow-up period until relapse/progression. Subjects will begin the long term follow-up period after they have completed the EOT visit.

After relapse/progression, subjects will be followed for overall survival and subsequent anticancer therapies.

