12.4 Statistical analysis plan

All analyses will be done in accordance with the intention-to-treat principle in all patients who have initiated the study treatment, when the last patient is 100 days post transplantation or has gone 'off-protocol'.

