12.4.1 Primary endpoint

The primary endpoint is the probability of serious viral infections up to 100 days after transplantation for patients alive relapse-free at 100 days. This endpoint will be analyzed in a poisson regression model including treatment arm and the stratification factors used in the randomization.

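### Section 10.7 stops outcome collection after graft failure or a major protocol violation, contradicting 10.3.4 and leaving part of the primary endpoint window unobserved for patients whom the analysis still includes

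*Protocol*

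**What the plan says.** Section 10.7 gives four reasons for going off study: death, "Major protocol violation", graft failure, and relapse/progression. It continues: "Patients who are withdrawn from the study treatment for other reasons than death will be followed only for overall survival". Data already obtained from patients withdrawn "for other reasons than withdrawal of their consent will be used for statistical analysis".

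Section 10.3.3 adds that if a patient discontinues before day 100, "all assessments planned for the regular Day 100 visit should be performed at time of discontinuation". Section 10.3.4 sets a different rule: "All enrolled subjects will be followed in the long term follow-up period until relapse/progression". Only after that point does it narrow follow-up to survival and subsequent therapies.

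On analysis, section 12.4 states: "All analyses will be done in accordance with the intention-to-treat principle in all patients who have initiated the study treatment", timed for "when the last patient is 100 days post transplantation or has gone 'off-protocol". Section 12.4.1 defines the primary endpoint as the "probability of serious viral infections up to 100 days after transplantation for patients alive relapse-free at 100 days".

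**The concern.** A patient with graft failure or a protocol violation can be alive and relapse-free at day 100. Such a patient is in the analysis set of 12.4 and in the primary endpoint set of 12.4.1, yet 10.7 tells the site to collect nothing but survival. A site cannot obey both 10.7 and 10.3.4. No later analysis plan can repair this, because it concerns data that sites are told not to collect.

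The gap need not be neutral between arms. Both triggers arise after randomisation, and the trial is open label. Section 9.3 names graft failure as the main risk of too low fludarabine exposure, and section 9.2.1 reports more graft failures at lower exposures (p=0.03). Arm B is the arm designed to reduce exposure. At stake are the validity of the day-100 comparison and the later outcomes of patients with the very complication that the protocol singles out.

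**Working it through.** **Inputs.** Section 12.1: 42 evaluable patients per arm, infection proportions 40/90 = 0.444 (A) and 15/90 = 0.167 (B), two-sided 5%, pooled Z test, stated power 81%, 15% extra per arm. Section 10.2.3: primary graft failure is judged at day +28. Section 4.1.2: no graft failures in 75 patients on standard dosing. The protocol gives no expected number of graft failures or major violations, so every count or percentage of off-study patients below is an assumption.

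**1. The plan's own figure.** n = [1.960·√(2·p̄·(1−p̄)) + 0.842·√(pA(1−pA) + pB(1−pB))]² / (pA−pB)², with p̄ = 0.3056. This gives (1.277 + 0.523)² / 0.2778² = 3.238/0.0772 = 41.97, so 42 per arm. Power at 42 is 80.0%, close to the stated 81%. Then 42 × 1.15 = 48.3, rounded up to 49 per arm and 98 in total. The design reproduces.

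**2. Length of the gap.** From day +28 to day 100 is 100 − 28 = 72 days. The early-termination visit in 10.3.3 captures what happened before it, but cannot show what happens afterwards.

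**3. What is kept and what is lost under 10.7.**
- Kept: infections up to discontinuation and overall survival. For a patient who leaves because of graft failure, the graft-failure endpoint and the EFS event have already occurred.
- Lost: later viral infections to day 100, chronic GVHD, immune reconstitution, and later relapse status, without which a death cannot be classified as NRM.

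**4. Bounds on the primary contrast.** Let k of the 42 evaluable patients in each arm have unknown status, with x known infections in the arm. The arm's risk lies between x/42 and (x+k)/42, so the risk difference can lie anywhere in an interval of width 2k/42:
- k = 1: 2/42 = 4.8 points
- k = 2: 4/42 = 9.5 points
- k = 4: 8/42 = 19.0 points

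The planned difference is 44.4 − 16.7 = 27.8 points.

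**5. Loss of precision.** If the k patients per arm are dropped instead, power is 79.0% (k = 1), 78.0% (k = 2), 75.8% (k = 4) or 73.5% (k = 6).

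**6. Possible bias.** Suppose that only arm B is affected, that unobserved infections count as none, and that the true risk is 44.4% in both arms.
- 5% of arm B off study, all their infections missed: apparent benefit 0.444 × 0.05 = 2.2 points. The chance of a false finding in favour of B rises from 2.5% to 4.0%.
- 10% off study, all missed: 4.4 points, and 6.1%.
- If half of their infections occur before discontinuation and are recorded, these become 1.1 points and 3.2%, and 2.2 points and 4.0%.

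**The case against.** The best defence is that the damage is limited. Sections 10.3.3 and 10.7 keep everything up to discontinuation, survival follow-up continues, and graft failure is itself a counted endpoint and an EFS event. Section 10.3.4 already orders continued follow-up, so sites may in practice collect the data. Section 11.2.2 runs adverse event reporting to day 100 without excepting off-study patients, and section 12.2 includes all patients in the safety analysis. The 15% inflation covers non-evaluability for other reasons. With no graft failures in 75 patients, few may be affected.

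Most of this stands as a limit on size; it does not remove the contradiction. Adverse event reporting does not fill the primary endpoint: CMV, EBV and BK cystitis are carried on the infection CRF instead, and other events are reported only from CTCAE grade III, whereas the endpoint starts at grade 2 of Appendix E. Inflation protects power, not against selective loss. The cohort of 75 received standard dosing, so it says little about arm B.

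Some stronger readings are tempting, but the protocol does not support them:
- A reader might infer that intention-to-treat analysis becomes impossible. Patients can still be analysed as randomised, with partly incomplete outcomes.
- A reader might infer that the loss must fall mainly on arm B. Section 14.2 names GVHD as well as graft failure as a possible added risk. Both arms have conditioning, graft and prophylaxis steps that can be violated, and section 8.3 permits the formula in arm B when TDM is unavailable. Imbalance is possible, not established.
- A reader might add that graft failure itself raises viral infection risk. The protocol does not say so.
- A reader might add the unobserved infections to arm B's rate and conclude that power collapses. That calculates power for a smaller true effect, not the consequence of missing follow-up.

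**Conclusion.** The point holds as an internal contradiction with a real but unquantified effect on the primary endpoint. Section 10.7 conflicts with 10.3.4 and stops infection follow-up in patients whom 12.4 and 12.4.1 still analyse. After primary graft failure as defined in 10.2.3, up to 72 of the 100 endpoint days can be unobserved. The loss may be informative.

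The number affected cannot be derived from the protocol. With 1 to 4 such patients per arm, the worst-case uncertainty of 4.8 to 19.0 points is a material share of the planned 27.8-point difference, while the power cost of dropping them is only about 1 to 4 points. These bounds assume that none of the k patients had a recorded infection before discontinuation, so the true uncertainty would be no larger. The main issue is therefore possible bias, not sample size.

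Relapse is a separate matter. Relapsed patients fall outside the primary set in 12.4.1, and 10.3.4 also moves them to survival follow-up, so nothing is lost there from the primary analysis as defined.

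**What to change.** Reconcile 10.7 with 10.3.4 and 12.4 by separating going off treatment from stopping outcome collection. State that, unless consent is withdrawn, patients with graft failure or a major protocol violation stay on the infection CRF to day 100 and on the outcome schedule to 12 months or until relapse/progression, and are analysed in the arm to which they were randomised. Bring the early-termination visit in 10.3.3 and the analysis trigger in 12.4 into line, so that going off protocol before day 100 does not close a patient's endpoint window. This concerns data collection only and leaves clinical management of these patients untouched.

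The cost is an amendment to the wording and a few extra CRF entries. The Schedule of Assessments already describes CMV and EBV PCR for a year as standard care. The change has to be made prospectively, because infections not recorded at the time may not be recoverable.

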6. STUDY DESIGN

This is a multicenter prospective, open label randomized, phase II study (UMCU (Utrecht), LUMC (Leiden), Johannes Gutenberg University (Mainz)). Patients with hematological malignancies according to the inclusion criteria with a matched related donor or a matched unrelated donor, are treated with a $\alpha\beta$ TCR / CD19 depleted allo-SCT. Conditioning regimes are depicted on 8.3 which differ only in:

Arm A: Fludarabine based on classical dosing

Arm B: Individualized fludarabine aimed to avoid overexposure (section 9)

All other interventions, except for alternate dosing of fludarabine in arm B, are considered as standard of care. All subjects will complete the end of treatment visit at day 100. After day 100, subjects will enter an extended follow-up of 1 year.

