12.2 Safety

With respect to safety, a yearly report as described in 11.5 and 11.7 will be submitted to the EC and DSMB. In case 20 patients reach the 100 days follow-up before 1 year, the DSMB will be informed earlier. The yearly report will contain NRM, OS and relapse rates. In addition we will report the reportes (S)AEs and SUSARs. All patients will be considered in the safety analysis. Patients will be closely followed for unexpected toxicities and, if any serious side effects are observed, the investigators will reevaluate the appropriate course for the study. At the conclusion of the study, all unexpected toxicities will be summarized and reported. If the DSMB recommends to stop the study based on the safety outcomes, the sponsor (UMCU) Version 1.1 | 02 AUG 2018

will follow the advice of the DSMB or discuss with the EC requirements for continuation of the study.

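### Section 10.7 by implication drops the data of patients who withdraw consent, including data recorded before they withdrew, against the analysis populations in 12.2 and 12.4

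*Protocol*

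**What the plan says.** Section 10.7 of the protocol ends with two rules. The first: "Patients who are withdrawn from the study treatment for other reasons than death will be followed only for overall survival". The second limits analysis to data from patients who stopped "for other reasons than withdrawal of their consent will be used for statistical analysis". No other section says what happens to data recorded before consent was withdrawn.

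The analysis sections make no such exception:

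- Section 12.4: "All analyses will be done in accordance with the intention-to-treat principle in all patients who have initiated the study treatment".
- Section 12.2: "All patients will be considered in the safety analysis".

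Three further places bear on the point. Section 10.5 states: "Subjects can leave the study at any time for any reason if they wish to do so without any consequences". Section 10.3.3 asks for the full set of day-100 assessments "If a patient prematurely discontinues the study because of any reason before Day 100", to be entered as an early termination visit. Section 6 describes a "multicenter prospective, open label randomized, phase II study", so patients and clinicians know the arm.

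**The concern.** Withdrawing consent normally stops further data collection. It does not by itself require that earlier observations leave the analysis. Section 10.7 makes no such distinction, so a programmer following it would remove the patient's whole record.

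That matters here because of timing. Fludarabine is given on days -5 to -2 (section 8.3), while adverse events are reported from the start of conditioning until day 100 (section 11.2.2). A patient who withdraws after transplant has normally had the full randomised exposure, and may already have a graded viral infection, reportable toxicity and measured drug levels. In an open-label trial the decision to leave can depend on the known arm and on the clinical course. Removing recorded events is then potentially informative, and it takes away safety data after exposure to the drug under test.

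**Working it through.** **1. Does the text exclude these patients?** The sentence sorts withdrawn patients into those leaving because consent was withdrawn and all others, and says that data from the others are used. If data from both groups were used, the qualifier would do nothing. Exclusion is therefore the plain reading, though by implication only.

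**2. Side by side, for a treated patient who withdraws consent before day 100**

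| Section | Consequence |
|---|---|
| 12.4 | In every analysis, because treatment was started |
| 12.2 | In the safety analysis |
| 10.3.3 | Day-100 assessments done at discontinuation and recorded |
| 10.7 | Data not used |

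The last row cannot be followed together with the first two, and it leaves the early termination visit without use. Section 10.2.2 points the same way as 12.2: patients who die before infusion leave the survival analyses but are still evaluated for serious adverse events.

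**3. The plan's own sample size (section 12.1).** Inputs: failure rates pA = 40/90 = 0.4444 and pB = 15/90 = 0.1667, two-sided 0.05, pooled Z test, n = 42 per arm.

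- Mean rate 0.3056. Null SE = √(2 × 0.3056 × 0.6944 / 42) = 0.1005. Alternative SE = √((0.4444 × 0.5556 + 0.1667 × 0.8333) / 42) = 0.0958.
- Power = Φ((0.2778 − 1.96 × 0.1005) / 0.0958) = Φ(0.843) = 0.800, against the stated 81%.
- 42 × 1.15 = 48.3, so 49 per arm and 98 in total, as stated.

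The design figures are reproduced, and the fix changes none of them.

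**4. How much could deletion matter?** The protocol gives no rate of consent withdrawal, so everything below rests on assumed numbers. P-values are from the pooled Z test.

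- *Unselective loss.* Losing 1, 2, 3, 4 or 5 evaluable patients per arm lowers power from 0.80 to 0.79, 0.78, 0.77, 0.76 or 0.75.
- *Two infected patients lost from arm B only, planned rates.* 42 × 0.1667 = 7 events. 7/42 = 16.7% becomes 5/40 = 12.5%, which is 4.2 points, or a quarter of the full rate. Against 19/42 in arm A, p goes from 0.005 to 0.001, so the conclusion does not change.
- *The same loss with a smaller effect.* 17/42 against 10/42 gives p = 0.102. Dropping one infected arm B patient gives 0.069 and dropping two (8/40) gives 0.044.
- *About a quarter of infected patients lost in both arms.* 19/42 against 7/42 (45.2% − 16.7% = 28.6 points) becomes 14/37 against 5/40 (37.8% − 12.5% = 25.3 points). The difference shrinks.
- *No true difference (44.4% in both arms), loss of infected patients from arm B only.* The two-sided rejection rate is 0.061 with no loss, 0.067 if 15% of them are lost (2.8 patients on average) and 0.097 if 25% are lost (4.7 patients).

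The effect can go either way, and is small unless losses are several and one-sided.

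**The case against.** The strongest reply has four parts.

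*The exclusion is inferred.* The sentence says whose data will be used; it never says that other data are deleted. It also speaks of withdrawal from study treatment, which is over by day -2. Both observations are correct. But the sentence sits under a heading on going off study, beside graft failure and relapse, which typically occur after treatment, and no other text keeps the data. Loose scope is a reason to reword it.

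*The primary analysis may lose these patients anyway.* Section 12.4.1 is restricted to patients alive and relapse-free at day 100. Someone who withdraws fully on day 60 cannot be shown to meet that condition, so a day-40 infection could drop out even if 10.7 were rewritten. This stands. A reader might infer that 10.7 by itself biases the primary comparison, and the documents do not support that. The harm that can be tied to 10.7 falls first on the safety, exposure and secondary analyses.

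*The arm B example is one-sided.* A reader might infer that the arm B rate would be understated by a quarter in favour of the new dosing. Nothing in the protocol says how often consent is withdrawn or that it depends on arm, and loss in proportion to infections would shrink the difference. This stands too.

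*Details of this kind belong in an analysis plan.* True of a rule left open, but here the protocol states a rule, and the rule conflicts with its own analysis populations.

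A reader might also see a second contradiction within 10.7, with survival follow-up ordered in one sentence and made unusable in the next. That depends on reading the follow-up sentence as covering consent withdrawers. They are not in the section's list of reasons, and patients who choose to leave are dealt with in 10.5. It is better treated as loose drafting.

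**Conclusion.** The point holds as an inconsistency that should be corrected. By plain implication 10.7 leaves out the data of consent withdrawers, with no distinction between data before and after withdrawal, and this cannot be reconciled with 12.4 and 12.2. What is at risk is information already collected after randomised exposure: adverse events, infections, drug levels and secondary outcomes.

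The bias cannot be sized or signed from the documents. The calculations assume 42 evaluable patients per arm and invented numbers of withdrawals; they show that a few selective losses could move a borderline result, and no more than that. For the primary endpoint, the restriction in 12.4.1 is a separate cause of loss and has to be settled at the same time.

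**What to change.** - **10.7, aligned with 10.5, 12.2 and 12.4:** keep data recorded up to the date of consent withdrawal and analyse them in the randomised arm, as far as the consent given and applicable law allow. Keep recorded adverse events and deaths in the safety analysis. Limit later survival follow-up to patients who agree to it.
- **Time-to-event and cumulative-incidence analyses:** censor at the date of withdrawal.
- **Primary endpoint:** reconcile 5.1 (cumulative incidence to day 100), 12.1 (success means infection-free, alive and relapse-free) and 12.4.1 (conditional on being alive and relapse-free at day 100), so that a severe viral infection recorded before withdrawal counts. State how a withdrawn patient without an event and with unknown day-100 status is handled. Censoring does not fit the conditional Poisson analysis as written, so 12.4.1 itself needs a change.
- **Case report form:** record whether the patient withdraws from study procedures only or from all further data collection.

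The cost is a few sentences across these sections, one form field and possibly a line in the patient information. No extra patients or visits are needed.

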10.8 Premature termination/alteration of the study

The sponsor (UMCU) may decide to terminate the study prematurely based on the following criteria:

- There is evidence of an unacceptable risk for study patients (i.e. safety issue)
- The DSMB recommends ending the trial based on viable arguments (e.g. insufficient enrollment of patients). Statistical analyses for all decisions are available under section 12.

11. SAFETY REPORTING

11.1 Temporary halt for reasons of subject safety

In accordance to section 10, subsection 4, of the WMO, the sponsor (UMCU) will suspend the study if there is sufficient ground that continuation of the study will jeopardise subject health or safety. The sponsor will notify the accredited ethics committee (EC) without undue delay of a temporary halt including the reason for such an action. The study will be suspended pending a further positive decision by the accredited EC. The investigator will take care that all subjects are kept informed.

11.2 Adverse events

11.2.1 Definition AE

Adverse events (AE) are defined as any undesirable experience occurring to a subject during the study, whether or not considered related to the study treatment. All adverse events reported spontaneously by the subject or observed by the investigator or its staff will be recorded, excluding exceptions defined in section 11.2.2.

11.2.2 Reporting AEs

Adverse events will be reported from the start of the conditioning until 100 days following stem cell infusion. Adverse events have to be reported on the Adverse Events case report form (CRF). Adverse events will be scored according to the NCI Common Terminology Criteria for Adverse Events (CTCAE), version 4.03.

All Adverse Events have to be reported, with the exception of:

- A pre-existing condition that does not increase in severity; the pre-existing condition should be reported on the baseline concomitant diseases CRF
- AEs of CTCAE < grade III
- Mucositis CTCAE < grade IV
- All hematological toxicities (unless SAE), alopecia, nausea and vomiting
- AEs directly contributable to ATG infusion (e.g. hypotension, fluid overload); unless SAE.
- AEs directly contributable to stem cell infusion / infusion blood products resolving < 24 hours (e.g. hypotension, fever); unless SAE.
- Neutropenic fever without a clinical substrate, responding to i.v. antibiotics < 72 hours.
- GvHD, to be reported on specific GvHD CRF
- Viral infections (CMV/EBV/BK cystitis), to be reported on infection CRF.

